11. STATISTICAL CONSIDERATION
12. REPORTING REQUIREMENT
13. REFERENCES
14. APPENDIX

INFORMED CONSENT

Study Chairman: [name].

Collaborators:

~~[name]~~, M.D.

~~[name]~~, M.D.

~~[name]~~, M.D.

~~[name]~~, M.D.

~~[name]~~, M.D.

~~[name]~~, M.D.

~~[name]~~, M.D., Ph.D.

~~[name]~~, Ph.D.

1.0 OBJECTIVES:

1.1 Primary:

To evaluate the event free survival (EFS) following therapy with rituximab plus ABVD or standard ABVD in patients with newly diagnosed classical Hodgkin lymphoma who have poor prognosis defined as International prognostic score (IPS) of > 2.

1.2 Secondary:

1.2.1 To compare the effect of the two treatment arms on PET scan results after 2 cycles of therapy

1.2.2 To compare the effect of the two treatment arms on the level of circulating malignant Hodgkin stem cells

2.0 BACKGROUND:

2.1 Hodgkin lymphoma: The world health organization (WHO) classification of Hodgkin lymphoma (HL) distinguished between two major subtypes, classical HL and nodular lymphocyte predominant HL.[1] Approximately 95% of patients with HL will have the classical HL histology, which is characterized by the presence of rare malignant Hodgkin and Reed Sternberg (HRS) cells among an overwhelming number of benign reactive cells. In recent years, new studies shed more light on the biologic and molecular features of HRS cells providing hopes that new targeted therapy may be developed to enhance the cure rate and to reduce treatment-related toxicity.

2.2 Current standard therapy of classical HL: Based on several randomized studies comparing ABVD (doxorubicin, bleomycin, vinblastine, and dacarbazine) with other multi-drug regimens, ABVD became the most widely used combination regimen for the treatment of patients with advanced HL.[2-4] Chemotherapy alone (6-8 cycles) is usually considered to be sufficient for the treatment of patients with advanced stage classical HL. However, involved field radiation therapy is frequently added at the end of chemotherapy to areas of bulky disease. This combined modality approach has been recently compared to chemotherapy (MOPP/ABV) alone in a randomized trial in patients with advanced stage classical HL, and showed no survival advantage, especially in those who achieved complete remission after the completion of chemotherapy.[5] Furthermore, meta-analysis review of fourteen clinical trials comparing chemotherapy with combined modality also showed no survival advantage for those receiving the combined modality approach.[6] Newer treatment programs such as Stanford-V and BEACOPP have shown successful results, but remain less widely used compared with ABVD.[7-9] Although BEACOPP has been shown to be superior to ABVD-like regimens in large scale randomized trials, the superiority of Stanford-V over standard ABVD has not yet been established.[10] Because ABVD may cure only 50-65% of patients with poor risk advanced stage HL, more intensive programs such as BEACOPP may add benefit, despite the increased toxicity. Patients with good risk features have a high cure rate with ABVD, so the use of more intensive and more toxic regimens in this patient population should be used with caution, and preferably within a clinical trial.

2.3 The International Prognostic Index (IPS): HL is staged according to the Cotswold modification of the Ann Arbor staging system.[12] Only imaging studies and bone marrow biopsies (clinical staging) are used for stage assignment and treatment planning. The international prognostic score (IPS) was developed to further guide therapy of patients with advanced stage HL.[11] In this model, seven factors are used [Table 1]. Using this model, 42% of patients with advanced stage HL are expected to have an IPS score of >2 (3-7), and those patients are expected to have a 55% 5-year freedom from progression with ABVD-like therapy. In contrast, patients with IPS score 0-2 are expected to have 74% 5-year freedom from progression. Thus, patients with IPS score of > 2 have a poor outcome with current standard therapy, and will be included in this proposed study.

Table 1	
International Prognostic Score (IPS) for Advanced HL[11]	
1. Sex :	male
2. Age:	≥ 45
3. Stage:	IV
4. Hemoglobin	<10.5 g/dl
5. WBC:	≥ 15,000/
6. Lymphocyte count	< 600/ or < 8% of WBC
7. Serum albumin	< 4 g/dl

2.4 Rational for using rituximab for the treatment of classical HL:

2.4.1 Role of reactive B-cells in the microenvironment: HRS cells are surrounded by an overwhelming number of reactive cellular infiltrate. These reactive cells are not bystander cells, as once thought of. In contrast, they frequently provide survival signals to HRS cells.[13] The role of the microenvironment in supporting the survival and growth of HRS cells is best illustrated by the difficulty of establishing HRS-derived cell lines. Once HRS cells are taken out of the microenvironment, it is extremely difficult to grow them in culture. It is, therefore, ironic that the host own immune cells are providing survival factors to the malignant cells, creating an “immune-betrayal” phenomenon. Therefore, we hypothesized that eliminating these reactive cells from the microenvironment may deprive HRS cells from critical survival factors and may lead to their growth arrest and death.[13]

2.4.2 The putative Hodgkin stem cells are CD20+ cells: The rationale for using rituximab in classical HL was recently strengthened by the identification of putative HL stem cells that express CD20.[14] In a landmark study, a group from Johns Hopkins University studied HL cell lines (L428, KM-H2) and found that each line contained a small (<5%) subpopulation of cells that did not express the typical HRS markers CD15 and CD30. Instead, this small subpopulation resembled memory B cells (CD19+CD20+CD27+) and possessed most of the clonogenic capacity of the HL cell lines. Using Aldefluor, a fluorescent aldehyde that is a substrate for aldehyde dehydrogenase (ALDH) that is highly expressed in both normal and malignant stem cells, the clonogenic subpopulation within the HL cell lines also expressed high ALDH activity, while the predominant HRS cells exhibited low ALDH activity. Subsequently, the same investigators examined CD19+ cells that were isolated from the marrow or blood of 5 HL patients. The ALDH-high CD19+ cells were a highly enriched population of immunoglobulin (Ig) light chain-restricted CD27+ memory B cells that represented 0.7 to 3% of the circulating CD19+ cells. These ALDHhigh CD19+ cells also displayed clonal Ig gene rearrangement by polymerase chain reaction (PCR) amplification. In two of these patients, CD15+CD30+ HRS cells were isolated from a fresh diagnostic lymph node and contained the same clonal Ig gene rearrangement as the circulating ALDHhigh CD19+ B cells. Thus, clonotypic memory B cells can be found in both HL cell lines and

patients. These data suggest that these clonotypic memory B cells circulate in relatively high numbers even in early stage patients, and may represent the HL stem cells.[14]

2.5 Results with rituximab plus ABVD: The clinical activity of rituximab in patients with relapsed classical HL (irrespective of CD20 expression by HRS cells) was recently examined by our group at M. D. Anderson Cancer Center, in which rituximab was used to deplete CD20+ reactive B lymphocytes from HL microenvironment.[15] Twenty-two heavily pretreated patients with classical HL were treated with six weekly doses of rituximab. Five (22%) patients achieved partial or complete remissions, and eight additional patients had stable disease. Clinical remissions were observed in patients irrespective of CD20 expression by HRS cells, but were observed in patients whose disease was confined to the lymph nodes. In a follow-up study, we combined rituximab with ABVD (R-ABVD) chemotherapy to treat patients with newly diagnosed classical HL.[16, 17] In this phase II study, 65 patients with classical HL were treated with R-ABVD. With a median follow up of 32 months, the estimated event-free survival (EFS) is 82% and overall survival 100%. Importantly, the EFS was improved for all risk categories: for patients with a prognostic score of 0-1 the EFS was 92%, for score 0-2 was 86%, and for score 3-5 was 73% (Fig 1, Table 2).

Table -2 : Event free survival (EFS) observed in patients treated with R-ABVD compared to historical data with ABVD alone. EFS is shown in different groups according to IPS.

IPS Group	ABVD 3-year EFS	R-ABVD 3-year EFS
0-1	79%	95%
0-2	74%	87%
2	67%	76%
>1	60%	76.5%
>2	55%	77%
>3	47%	71%

[figure not shown]

Figure 1: Event free survival (EFS) in 65 patients treated with rituximab plus ABVD (R-ABVD); (Left) results are shown in 5 risk groups according to the international prognostic score (IPS). (Right) results are shown in patients with IPS score of 0-2 and > 2. The same data is shown in Table 2.

2.6: Role of early PET imaging in predicting treatment outcome: While the IPS may predict treatment outcome in patients with advanced HL, others have recently examined

the prognostic role of PET imaging after starting therapy. Using this approach, Hutchings and colleagues prospectively assessed the value of positron emission tomography with 2-[18F]fluoro-2-deoxy-D-glucose (FDG-PET) after two cycles of chemotherapy for prediction of progression-free survival (PFS) and overall survival (OS) in Hodgkin lymphoma (HL).[18] Seventy-seven consecutive, newly diagnosed patients underwent FDG-PET at staging, after two and four cycles of chemotherapy, and after completion of chemotherapy. After two cycles of chemotherapy, 61 patients had negative FDG-PET scans and 16 patients had positive scans. Eleven of 16 FDG-PET-positive patients progressed and 2 died. Three of 61 FDG-PET-negative patients progressed; all were alive at latest follow-up. Survival analyses showed strong associations between early FDG-PET after two cycles and PFS ($P < .001$) and OS ($P < .01$). Thus, a positive early interim FDG-PET is highly predictive of progression in patients with advanced-stage HL.

- 2.7 **Proposal:** based on the encouraging phase-II data from MDACC, we propose to confirm these results in a randomized study focusing on patients with poor risk features (IPS score > 2). Furthermore, we will compare the effect of these two treatment arms on PET imaging after 2 cycles of therapy, and on the level of circulating HL stem cells, and correlate these results with EFS.

3.0 DRUG INFORMATION:

Rituximab

Rituximab is a genetically engineered, chimeric, murine/human monoclonal antibody directed against the CD20 antigen found on the surface of normal and malignant pre-B and mature B cells. The antibody is an IgG₁ κ immunoglobulin containing murine light- and heavy-chain variable region sequences and human constant region sequences. Rituximab is composed of two heavy chains of 451 amino acids and two light chains of 213 amino acids (based on cDNA analysis) and has an approximate molecular mass of 145 kD. Rituximab has a binding affinity for the CD20 antigen of ~ 8.0 nM.

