- b. Known HIV infection.
- c. Pregnant women and women of child bearing age who are not practicing adequate contraception
- d. Prior chemotherapy or radiation therapy.
- e. Severe pulmonary disease as judged by the PI including COPD and asthma
- f. Active infection requiring treatment with intravenous therapy
- g. Presence of CNS lymphoma
- h. Concomitant malignancies or previous malignancies within the last 5 years (exception made for adequately treated basal or squamous cell carcinoma of the skin or carcinoma in situ of cervix)

- 5.3 Total doses of rituximab will be 6 and of ABVD will be 12 doses (6 cycles). Rituximab may be given on the same day of ABVD therapy. For cycle 1 only, Rituximab may be given on day 2, if time constraints do not allow both ABVD and Rituximab to be given on day 1. This research study protocol allows the subject to receive up to 6 infusions of rituximab. Even if the treatment is shown to be of benefit, additional infusions of rituximab beyond that allowed in the protocol cannot be given to the subject while she/he is participating in this study.

Patients of MDACC and randomized to the ABVD arm, will be allowed to receive treatment with their local MD. Patients of MDACC and randomized to the RABVD arm, will be required to receive all Rituximab containing regimens at MDACC but can receive standard ABVD with local MD. (see appendix A).

- 5.4 A summary of the two treatment arms is shown in the table below.

Drug	Dose		Route
	Arm-A	Arm-B	
Rituximab	375 mg/m ²	---	iv
Adriamycin	25 mg/m ²	25 mg/m ²	iv
Bleomycin	10 U/m ²	10 U/m ²	iv
Velban	6 mg/m ²	6 mg/m ²	iv
DTIC	375 mg/m ²	375 mg/m ²	iv

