7.0 EVALUATION DURING THE CHEMOTHERAPY ADMINISTRATION

- 7.1 CBC with differential at the beginning of each ABVD dose (within 2 days)
- 7.2 Monthly serum electrolytes
- 7.3 Repeat imaging studies every 2 cycles of ABVD.
- 7.4 PET scan after 2 cycles of therapy (approximately 2 months), and every 2 cycles until it becomes negative (if clinically indicated) .
- 7.5 Repeat bone marrow biopsy/aspirate if was positive prior to starting therapy at the end of ABVD therapy.

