- Active HBV infection or hepatitis (Subjects who are carriers of hepatitis B at the time of discontinuation from study treatment will continue to be followed for clinical and laboratory signs of active HBV infection and for signs of hepatitis)
- Severe or life-threatening anaphylaxis or hypersensitivity reaction
- Inability of subject to comply with study requirements
- Determination by the investigator that it is no longer safe for the subject to continue therapy
- Increasing disease, at any time during treatment or of less than PR after a minimum of 6 courses of therapy. Sometimes, a patient's disease will

progress so rapidly that it is appropriate to change therapy after a single course. Patients who are not responding will be considered failures on this regimen and if medically stable will be offered an alternative regimen. Patients who develop unacceptable toxicity should be removed from the study.

- Grade 3 or 4 non-hematologic toxicity that are not predicted by ABVD or R-ABVD (alopecia, nausea/vomiting, neuropathy).
- Patient's refusal to continue therapy.

11.0 STATISTICAL CONSIDERATION:

This is a trial to study the chemotherapy ABVD (Adriamycin, Bleomycin, Vinblastine, and Dacarbazine) with or without rituximab in treating patients with Hodgkin Lymphoma. Patients will be enrolled into the study at the accrual rate of 3 patients per month with an additional thirty-nine months follow-up period.

Objective

The primary objective of the study is to evaluate the efficacy of the combination regimen of rituximab and ABVD chemotherapy (R-ABVD) and ABVD alone measured as event-free survival (EFS).

Sample Size and Power

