Appendix A
Outside Physician Participation During Treatment

1 MDACC Physician communication with the outside physician is required prior to the patient returning to the local physician.

This will be documented in the patient record

2 A letter to the local physician will outline the patient's participation in the clinical trial and will request local physician agreement to supervise the patient's care

3 Protocol required evaluations outside MDACC will be documented by telephone, fax or e-mail. Fax and/or e-mail will be dated and signed by the MDACC physician, indicating that they have reviewed it.

4 Changes in drug dose and/or schedule must be discussed with and approved by the MDACC physician investigator, or their representative prior to initiation, and will be documented in the patient record.

5 A copy of the informed consent, protocol abstract, treatment schema and evaluation during treatment will be provided to the local physician.

6 Documentation to be provided by the local physician will include drug administration records, progress notes, reports of protocol required laboratory and diagnostic studies and documentation of any hospitalizations.

7 The home physician will be requested to report to the MDACC physician investigator all life threatening events within 24 hours of documented occurrence.

8 Patients will return to MDACC every 2 months for evaluation.

9 Patients randomized to the ABVD alone treatment group will be allowed to receive ABVD with their local MD. For those randomized to the Rituximab group, they will be allowed to receive ABVD at home with their local MD once they have completed the Rituximab component (ie. first 6 weeks). Rituximab must be given at MDACC.

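### The between-arm PET comparison after 2 cycles rests on a judged call, and no available section keeps the reader unaware of treatment arm or fixes where the scan is read

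*Combined protocol and SAP*

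**What the plan says.** Objective 1.2.1 is "To compare the effect of the two treatment arms on PET scan results after 2 cycles of therapy". Section 2.7 repeats it and adds that the PET results will be correlated with EFS.

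Section 7.4 schedules the scan: "PET scan after 2 cycles of therapy (approximately 2 months), and every 2 cycles until it becomes negative". It names no reader. The response table in section 9.0 uses the terms PET positive and PET negative without a scale or threshold. Section 11.0 has no analysis specific to PET; its general provision for categorical variables is the chi-square or Fisher's exact test.

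Section 11.0 introduces the study as follows: "This is a trial to study the chemotherapy ABVD (Adriamycin, Bleomycin, Vinblastine, and Dacarbazine) with or without rituximab". In the table in section 5.4, Arm B has a blank for rituximab, and no placebo appears.

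On place of treatment, section 5.3 says: "Patients of MDACC and randomized to the ABVD arm, will be allowed to receive treatment with their local MD". Patients there in the rituximab arm "will be required to receive all Rituximab containing regimens at MDACC but can receive standard ABVD with local MD". Appendix A item 9 lets them have ABVD at home "once they have completed the Rituximab component (ie. first 6 weeks"). Item 3 adds: "Protocol required evaluations outside MDACC will be documented by telephone, fax or e-mail". Item 8 brings patients back to MDACC every 2 months for evaluation, without distinguishing the arms.

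**The concern.** A PET call on a borderline scan is a reading, not a measurement. With no placebo described, whoever makes the call can know the arm from the treatment record or from the referring physician. If that knowledge shifts even a few borderline calls, the comparison in objective 1.2.1 is biased. A larger sample would not remove that bias, and the same call then enters the correlation with EFS.

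The plan also leaves open where the call is made. Item 3 of Appendix A accepts evaluations done elsewhere and reported by telephone, fax or e-mail, so calls could come from several readers using different working standards.

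**Working it through.** **1. Is there a safeguard in the text?**

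| Place | Reader named | Reader unaware of arm | Positivity rule |
|---|---|---|---|
| 7.4 | no | no | no |
| 9.0, response table | no | no | positive/negative only |
| 11.0 | no | no | no |
| Appendix A | no | no | no |

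Sections 5.0 to 5.2 are not in the available text, so a masking statement there cannot be excluded.

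**2. Inputs.** The plan gives no figure for the PET comparison, so these are borrowed.
- Scans per arm: n = 54 (section 11.0), assuming one readable scan per patient.
- Positive rate after 2 cycles: 16/77 = 20.8%, from the PET study described in section 2.6. That cohort is described as consecutive newly diagnosed patients, not as IPS > 2, so 30% and 40% are also tried.
- Test: uncorrected chi-square at 3.841, or two-sided Fisher at 0.05.
- Shading: the number of calls moved by knowledge of arm. The documents give no value.

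**3. The plan's own figures for the primary endpoint**, as a check on n:
- HR = ln(0.77)/ln(0.55) = 0.437, as stated.
- Freedman events = (1.96 + 0.842)² × [(1 + 0.437)/(1 − 0.437)]² ≈ 51.2, rounded up to 52, as stated.
- 108/0.90 = 120, as stated.

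None of these uses the PET result.

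**4. How many calls turn exact balance into p < 0.05?** Expected positives per arm are 54 × 0.208 = 11.2, so start from 11 v 11. With p̄ = (a + b)/108, X² = (a − b)²/[108 p̄(1 − p̄)].
- 11 v 4 (7 changed in one arm): 49/12.92 = 3.79, not significant; Fisher p = 0.09.
- 11 v 3 (8 changed): 64/12.19 = 5.25, significant; Fisher p = 0.04.
- 15 v 7 (4 changed in each arm, opposite directions): 64/17.52 = 3.65, not significant; Fisher p = 0.09.
- 16 v 6 (5 changed in each arm): 100/17.52 = 5.71, significant; Fisher p = 0.03.

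**5. What does shading do to the false-positive rate?** Let true positivity be p in both arms. For k calls shaded in the R-ABVD arm only, the read rates are p and p − k/54. For k calls shaded in each arm, in opposite directions, they are p + k/54 and p − k/54. The false-positive rate is the sum of Bin(a; 54, p₁) × Bin(b; 54, p₂) over all pairs (a, b) that the test rejects.

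At p = 20.8%:

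| Shading (mean number of calls) | Chi-square | Fisher |
|---|---|---|
| none | 5.1% | 2.7% |
| 1, one arm | 5.7% | 3.1% |
| 2, one arm | 7.8% | 4.5% |
| 3, one arm | 11.6% | 7.0% |
| 4, one arm | 17.4% | 11.2% |
| 2 in each arm (2/54 = 3.7 points) | 15.8% | 10.3% |
| 4 points in each arm (0.04 × 54 = 2.2 calls) | 17.7% | 11.8% |

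The effect is smaller at higher positive rates. With 3 to 4 calls shaded in one arm, chi-square gives 9.7–13.8% and Fisher 6.6–9.7% at 30% positive; at 40% positive they give 9.4–12.9% and 6.5–9.2%.

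**The case against.** The strongest reply concerns site. A reader might infer from section 5.3 and Appendix A that ABVD scans are read locally and R-ABVD scans at MDACC. The documents do not support that. What differs by arm is where drug is given, only for MDACC patients, and for about the first 6 weeks. No passage says that PET is read where drug is given. Item 8 returns patients in both arms to MDACC every 2 months, which matches the PET date in 7.4, and item 3 applies to both arms alike. This reply stands: a site difference between the arms in PET reading is not shown. What remains is that no passage ties the scan or its read to the return visit.

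A reader might also infer that a handful of shaded calls is enough to create a significant difference. It is not. From balance, 8 calls in one arm or 5 in each must change. Smaller numbers raise the probability of a false finding, which is a weaker statement. With Fisher's test, which the plan also allows, 2 calls shaded in one arm still leave the rate below 5%.

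Finally, this is a secondary comparison with no stated power or decision rule, and the discontinuation criteria in section 10.0 name no cycle-2 PET result. That limits the consequence, but it does not supply the missing safeguard.

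**Conclusion.** The gap holds in a limited form. Objective 1.2.1 depends on a judged call, no placebo is described, and none of the available sections on PET, response, statistics or outside care keeps the reader unaware of arm or fixes the place of reading. If calls were influenced by arm, shading 3 to 4 of them in one arm would raise the false-positive rate from 5% to about 12–17% (chi-square) or from 3% to 7–11% (Fisher). About 2 calls in each arm, in opposite directions, would raise it to about 16–18% or 10–12%.

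These figures rest on 54 scans per arm, 21% positivity borrowed from a different cohort, and an assumed amount of shading. They show sensitivity to bias and are not evidence that bias will occur. The primary EFS sample size is untouched. Severity is minor.

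**What to change.** In section 7.4 and Appendix A, state the following for both arms.
- The PET after 2 cycles is done at the enrolling centre, or its images are sent there, at the 2-month return visit that Appendix A item 8 already requires.
- That centre's usual reader calls it positive or negative against the baseline PET.
- The reader works from images labelled by study number only, without treatment arm, treating site or the treatment record. Leaving the arm off the request form is not enough if the reader can open the clinical record.
- One positivity rule, fixed in advance, is used for every scan.

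Use only that call for objective 1.2.1 and for the correlation with EFS. If sections 5.0 to 5.2 already contain a masking provision, refer to it in 7.4.

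The change needs no extra reader, scan or visit. Its cost is protocol wording, de-identification of images, and some image transfer for patients scanned elsewhere.
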